2.6.1.5 Dosing regimen of brolucizumab

The binomial proportion and 95% CI using the Clopper-Pearson method will be provided for patients who are maintained on an exclusive q12w interval following the loading phase through Week 48.

The number and percentage of q8w dose frequency patients will be presented along with 95% CI using the Clopper-Pearson method.

Duration of dose is defined as (date of last dose – start date of dose).

The summary statistics (n, mean, std, first quartile, median, third quartile, min and max) for duration of dose will be provided for patients who are maintained on an exclusive q12w interval following the loading phase through Week 48. In the study design the 3×4 -week dosing frequency, in initiation phase.

The above analysis will be done only on the study eye. The analysis will be performed on the FAS.

2.6.1.5.1 Predictive value of the first q12w cycle for maintenance of q12w treatment with brolucizumab

The probability of the first q12w interval will be derived from KM time to event analyses. KM plot will be provided. Detailed KM results will be presented including time (week), number of patients under risk at visit, number of patients with first q12w or discontinue at visit, probability of maintaining on q12w (survival probability) and 95% CI for maintaining on q12w.

Variable	Definition	
Start date	First date when patients on q12w interval	
Event	Fail maintain to q12w interval	
End date	Last date of initial q12w interval (before or on first start of q8w interval)	
Censoring (end date)	Completed/Discontinue with q12w	
Duration of time	(End date – start date) +1	

The above analysis will be done only on the study eye. The analysis will be performed on FAS.

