1.2 Study objectives and endpoints

Table 1-1 Objectives and related endpoints

Objectives	Endpoints	
Primary objectives	Endpoints for primary objectives	
To evaluate the short-term effect of brolucizumab on CNV lesion area as measured by OCT-A in nAMD patients.	Percentage change in CNV lesion area measured by OCT-A from Baseline to Week 12.	
Secondary objectives	Endpoints for secondary objectives	
To evaluate the long-term effects of brolucizumab on CNV morphology as measured by OCT-A in nAMD patients.	Percentage change in CNV lesion area measured by OCT-A from Baseline to Week 48.	
	Change in OCT-A features assessed by qualitative and quantitative criteria from Baseline by visit at Week 12 up to Week 48.	
To evaluate the effect of brolucizumab on anatomical parameters as assessed by SD- OCT and FA from Week 12 up to Week 48.	• Change in SD-OCT and FA features assessed by qualitative and quantitative criteria (e.g. CSFT, sub- and/or intraretinal fluid, sub-RPE fluid) from Baseline by visit up to Week 48.	
To evaluate the efficacy of brolucizumab up to Week 48 by assessing changes in BCVA.	Change in BCVA from Baseline up to Week 48.	
To estimate the proportion of patients treated at q12w frequency with brolucizumab.	• Proportion of patients who are maintained on an exclusive q12w interval following the loading phase through to Week 48.	
To estimate the predictive value of the first q12w cycle for maintenance of q12w treatment with brolucizumab.	• The probability of the first q12w interval for determining successful q12w maintenance at Week 48.	
To evaluate the time from last IVT injection in the initiation phase to first visit with no disease activity.	Time from last IVT injection in the initiation phase to first visit with no disease activity.	
To evaluate the safety of brolucizumab.	Incidence of AEs (serious and non-serious) reported in patients treated with brolucizumab.	

AEs= adverse events, BCVA= best corrected visual acuity, CNV= choroidal neovascularization, CSFT= central sub-field retinal thickness, FA= fluorescein angiography, IVT= intravitreal nAMD= neovascular age-related macular degeneration, OCT-A= optical coherence tomography-angiography, SD-OCT= spectral domain optical coherence tomography, sub-RPE= subretinal pigmented epithelium

2 Statistical methods

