2.6.1.6 Disease activity assessments

The number and percentage will be presented by visit for disease activity assessment.

The above analysis will be done only on the study eye. The analysis will be performed on FAS.

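### For the predictive value of the first q12w cycle, the plan gives one Kaplan-Meier curve with an unanchored start date and no estimate conditional on that cycle

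*SAP*

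**What the plan says.** Protocol Table 2-1 and SAP Addendum Table 1-1 list two separate secondary objectives on dosing. One is the proportion of patients kept exclusively on q12w. The other is the predictive value of the first q12w cycle, with the endpoint "The probability of the first q12w interval for determining successful q12w maintenance at Week 48".

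For these, Protocol 12.5.1 plans Clopper-Pearson proportions of q12w status at each disease activity visit and a Kaplan-Meier analysis of time to first q8w need, on the FAS.

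The SAP Addendum covers the first objective in 2.6.1.5: "The binomial proportion and 95% CI using the Clopper-Pearson method will be provided for patients who are maintained on an exclusive q12w interval". For the second, 2.6.1.5.1 states "The probability of the first q12w interval will be derived from KM time to event analyses", again on the FAS. Its definition table gives:

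- start date: "First date when patients on q12w interval"
- event: failure to maintain q12w
- censoring: "Completed/Discontinue with q12w"

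The listed output includes the number at risk, the probability of staying on q12w with its 95% CI, and "number of patients with first q12w or discontinue at visit". Section 2.6.1.6 adds "The number and percentage will be presented by visit for disease activity assessment", which concerns disease activity and not q12w status.

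**The concern.** A predictive value answers this question: given that a patient got through the first q12w interval without needing q8w, how likely is q12w to last to Week 48? Protocol 4.5 describes the pivotal result in that form, for patients free of disease activity in the initial interval. Under Protocol Section 3 a switch to q8w is permanent, so a patient who fails in the first cycle cannot count as maintained. The only informative value is the one among patients who pass.

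Neither document restricts the analysis to those patients, sets a landmark, or specifies a ratio of survival probabilities with an interval. Whether the one planned curve answers the objective therefore depends on its start date, which is not anchored. The documents offer three candidates:

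- **Week 8**, the last loading injection. Twelve weeks later is Week 20, and the Protocol summary places the Week 16 and Week 20 assessments inside the first q12w interval.
- **Week 16**, where Protocol Section 3 starts the q12w/q8w regimen. The event definition in SAP Addendum 2.1.1 also speaks of the investigator selecting q12w.
- **Week 20**, the first injection given after a 12-week interval.

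The Addendum revised the event and censoring rows of this section but left the start-date row as it stood in SAP Amendment 2.0. If Week 8 is used, the section named for the predictive value would report a number that mixes first-cycle failure with what the first cycle predicts.

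**Working it through.** **Plan's own figures.** The documents state none for this endpoint. The only input taken from them is N. Protocol 12.8.1: (1.96 × 35 / 5)² = 188.2, rounded up to 189; 189 / 0.90 = 210. Both reproduce. All rates below are assumptions.

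**Formula.** Let a be the share with no q8w need through Week 20, and c the probability of staying on q12w from Week 20 to Week 48 given that. Because the switch is permanent, marginal maintenance at Week 48 is a × c, and the predictive value is c = S(48)/S(20).

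**Illustration** (a = 0.65, c = 0.85, N = 210, no dropout):

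- Pass the first cycle: 210 × 0.65 = 136.5, taken as 136.
- Still on q12w at Week 48: 136 × 0.85 = 115.6, taken as 116.
- Marginal: 116/210 = 55.2%, Clopper-Pearson 95% CI 48.2 to 62.1.
- Conditional: 116/136 = 85.3%, 95% CI 78.2 to 90.8.

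With no dropout, a Kaplan-Meier curve from Week 8 ends at the same 55.2% as the Clopper-Pearson proportion already planned in 2.6.1.5.

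**Range.**

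- Hold c at 0.85. The marginal value is 0.75 × 0.85 = 0.638 with 25% first-cycle failure and 0.65 × 0.85 = 0.553 with 35%.
- Vary first-cycle failure over 25 to 35% and later failure over 10 to 20%. The marginal value runs from 0.65 × 0.80 = 0.52 to 0.75 × 0.90 = 0.675, and the conditional value from 0.80 to 0.90.
- One marginal value fits different predictive values: 0.68 × 0.75 = 0.51 and 0.60 × 0.85 = 0.51.

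**Effect of the start date.** This uses a second assumed set: q8w-need hazards of 0.20, 0.1875, 0.08 and 0.05 at Weeks 16, 20, 32 and 44.

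- S(16) = 0.80
- S(20) = 0.80 × 0.8125 = 0.650
- S(32) = 0.650 × 0.92 = 0.598
- S(44) = S(48) = 0.598 × 0.95 = 0.568

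| Start date | Printed Week 48 value | What it estimates |
|---|---|---|
| Week 8, all treated patients | 0.568 | marginal maintenance |
| Week 16, Week 16 failures having no start date | 0.568 / 0.80 = 0.710 | conditional on Week 16 only |
| Week 20, earlier failures excluded | 0.568 / 0.650 = 0.874 | the predictive value |

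A large simulated sample with 10% random dropout gave 0.568, 0.710 and 0.874. From the Week 16 curve the ratio is 0.710 / 0.8125 = 0.874, the same conditional value.

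The SAP duration formula (end − start + 1) shows the same dependence. A switch at Week 32 has a duration of 24 × 7 + 1 = 169, 16 × 7 + 1 = 113 or 12 × 7 + 1 = 85 days. If the origin is Week 20 and the whole FAS is kept, a Week 16 failure has −28 + 1 = −27 days.

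**Column label.** The event row counts failure to maintain q12w, and discontinuation while on q12w is censored. The output column instead counts first q12w together with discontinuation, so it matches neither rule.

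**The case against.** The strongest reply is that most of the information is already planned. The Kaplan-Meier table prints numbers at risk, events and q12w survival by visit. From a Week 8 or Week 16 origin a reader can divide S(48) by S(20) and approximate an interval from the counts after Week 20. If the start date means Week 20, the curve gives the answer directly. The Kaplan-Meier method is also the protocol's own, and the SAP follows it. All of this stands, and it limits the point: the conditional value is neither planned nor given an interval, but it is not out of reach. With dropout, the censored curve and the binomial proportion can also differ, so the overlap between them is close only when dropout is low.

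Three stronger readings are tempting, and the documents do not support them.

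- A reader might infer that q8w need first found at Week 44 cannot be an event, because eight weeks later is Week 52, after the study ends. The SAP dates the event by the start of a q8w interval ("Last date of initial q12w interval (before or on first start of q8w interval"). An interval triggered at Week 44 starts there; Week 52 is when it would end.
- A reader might see a conflict over the first q12w interval between the Protocol summary (Weeks 16 and 20) and Protocol Section 3 or SAP Addendum 1.1 (Week 16, then Weeks 20, 32 and 44). Counted from Week 8, Weeks 20, 32 and 44 are 12 weeks apart, and no text ends the first interval at Week 16.
- A reader might widen the assumed rates until marginal maintenance falls below 50%. Protocol 4.5 reports disease activity after loading in fewer than half of the pivotal patients, so such values lie outside the only background pattern the documents give.

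**Conclusion.** The point holds as an analysis gap for one secondary objective. No estimate conditional on the first cycle is planned, and the unanchored start date decides whether the planned curve shows marginal maintenance, maintenance given Week 16, or the predictive value itself. Under the assumed 35% and 15% failure rates, with 210 patients and no dropout, the marginal and conditional values are 55.2% and 85.3%, about 30 percentage points apart. The size depends on those assumptions; the difference in what is estimated does not.

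A reader might go further and conclude that the curve is certainly marginal, or that the objective cannot be answered. The documents do not support that: Week 8 is only one of three arguable origins, and the data needed are collected. The endpoint is descriptive, and no test, decision rule or primary result is affected.

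**What to change.** 1. In SAP Addendum 2.6.1.5.1, tie the Kaplan-Meier start date to a stated visit or injection. Keep the protocol's curve of time to first q8w need and label it as the marginal result.
2. Add a Week 20 landmark estimate: among FAS patients still on q12w after the Week 16 and Week 20 assessments, the probability of remaining on q12w to Week 48, with a 95% CI. State in one sentence that q8w need first found at Week 44 is handled as in Protocol 12.5.1.
3. Correct the output column so that it counts the event defined in the table, and show discontinuations in a separate column because they are censored.

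The cost is SAP wording and one extra table, with no new data. The landmark estimate rests on fewer patients than the FAS curve, about 136 of 210 under the assumed rates.

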2.6.1.6 Disease activity assessments

The number and percentage will be presented by visit for disease activity assessment.

The above analysis will be done only on the study eye. The analysis will be performed on FAS.

2.6.1.6.1 Duration of time from start of dose to till no disease activity

The median of duration of time is obtained from KM analysis along with 2-sided 95% CI will be presented. KM plots will be provided.

Detailed KM results will be presented including time (week), number of patients with no disease activity at visit, number of patients under risk at visit (with disease activity), probability of disease activity (survival probability) at visit and 95% CI at visit.

Variable	Definition		
Start date	Start date of start of IVT injection/ last IVT injection in the initiation phase		
Event	No disease activity		
End date of event	Date of first visit with no disease activity		
Censoring (end date)	Earliest of: • With disease activity until EOS		
Donation of time	• Early discontinuation		
Duration of time	(End date – start date) +1		

The above analysis will be done only on the study eye. The analysis will be performed on FAS.

2.8 Analysis of other efficacy variables

2.8.1 Color fundus photography

The number and percentage will be provided at Screening/Baseline, week 12 and end of study (Week 48) for below questions:

- Was color fundus photography performed? If not, then reason for not performed CFP.
- Presence of retinal hemorrhage in central subfield.
- Presence of subretinal hemorrhage in central subfield.
- Presence of fibrosis in the central subfield the diameter of 3000 μm.
- Presence of atrophy in the central subfield the diameter of 3000 μm.
- Is there subretinal blood affecting the foveal center point and/or >50% of total lesion.
- Presence of Vasculitis.

The above analysis will be done on both eyes. The analysis will be performed on the FAS.

2.8.2 Fundus autofluorescence (FAF)

The number and percentage will be provided at Baseline, week 4 and end of study (week 48) for below question.

- Fundus auto-fluorescennce performed at visit. If not then reason for not performed FAF.
- Presence of macular atrophy in the central subfield (center 1 mm circle).
- Presence of foveal atrophy.

The summary statistics (n, mean, std, median, min and max) of area of macular atrophy (mm²) will be presented at Baseline, Week 4 and Week 48 along with change from Baseline and percentage change from Baseline in FAF.

The above analysis will be done on the both eye. The analysis will be performed on FAS.

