**Table 8-1 Assessment schedule for the study eye**

Period	Treatment Period							Follow-up	
	Initiation Phase			q12w/q8w Phase				EOS  ETD 	M 
Visit	Screening/Baseline 					Interim Visits 	EOT‡		
	Day 1	Week 4	Week 8	Week 12	Week 16	Every 8 or 12 weeks according to treatment regimen	Week 40/ Week 44	Week 48	
Informed consent	X								
Inclusion/exclusion criteria	X								
Demography	X								
Medical history/current medical conditions	X								
Vital signs	X	X	X	X	X	X	X	X	
Prior/concomitant medications (including surgery and procedures)	X	X	X	X	X	X	X	X	X
Adverse events	X	X	X	X	X	X	X	X	X
BCVA score (ETDRS)	X	X	X	X	X	X	X	X	X
IOP	X							X	
Ophthalmic examination and imaging 	X	X	X	X	X	X	X	X	
SD-OCT 	X	X	X	X	X	X	X	X	
OCT-A 	X	X	X	X	X	X	X	X	
CFP 	X			X				X	
FAF	X			X				X	
FA 	X 			X					
ICG 	X			X					
Disease activity assessment	X	X	X	X	X	X	X	X	
Study drug IVT injection 	X	X	X		X 	X 	X 		
Telephone follow-up post injection 	X after 1st injection								

Note: Mandatory study visits are highlighted in grey.

Abbreviations: BCVA=best-corrected visual acuity, CFP=color fundus photography, EOS=end of study, ETDRS=early treatment diabetic retinopathy study, FA=fluorescein angiography, FAF=fundus autofluorescence, ICG=indocyanine green chorioangiography, IVT=intravitreal, OCT=optical coherence tomography

‡ The end of treatment will occur at either Week 40 or Week 44 according to the treatment schedule.

 The Screening/Baseline visit are performed on the same Visit.

 The number of weeks between visits will vary depending on the disease stability and length of intervals between injections as determined by disease activity assessment.

 Include slit lamp examination and fundus examination

 If FA has been made as required by the protocol during the 15 days prior to screening, FA does not need to be repeated on Screening/Baseline visit. In this case, FA image needs to be collected and reviewed by the CRC.

 ICG is optional at the discretion of the investigator. ICG should be performed at week 12 if it has been performed at Screening/Baseline.

 Treatment according to investigator decision based on disease activity assessment.

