### **8.3.2 Color fundus, fundus autofluorescence and fluorescein and indocyanine angiography**

**Color fundus photography (CFP), fundus autofluorescence (FAF) and fluorescein angiography (FA)** will be performed in the study eye at the visits indicated in the visit assessment schedule ([Table 8-1](#)). CFP, FAF and FA may be performed at other visits at the investigator's discretion but they are not mandatory for the study.

For the purpose of Screening/Baseline, FA images from a previous routine evaluation may be used as long as FA was performed within 15 days of the Screening/Baseline Visit.

An ICG could be performed at Screening/Baseline at the investigator discretion. ICG should be performed at week 12 if it has been performed at Screening/Baseline.

In case of premature discontinuation from the study, there is no need to repeat the CFP and FAF if there was a CFP and FAF performed within the previous 12 weeks, **except if there is significant disease worsening, in the opinion of the investigator.**

CFP and FAF assessments will not be reviewed by the CRC, the investigator will evaluate the images according to their standard of clinical practice.

FA and ICG assessments at Screening / Baseline and Week 12 will be reviewed by the CRC. The CRC will provide sites with a Study Manual and training materials for the specified study ocular images. All FA and ICG images will be forwarded to the CRC for independent standardized analysis and will also be forwarded to Novartis or designated CRO for storage.

Additional images will be taken in case of any signs of IOI. OCT, color fundus photography, FA and indocyanine green chorioangiography (preferably wide-field or with peripheral sweeps) should be performed for safety evaluation as described in [Section 8.4.3](#).

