- **Posterior segment (indirect fundus) examination** will be conducted by the investigator at the Screening/Baseline Visit for both eyes. An examination of the peripheral retina must also be conducted to ensure that the IVT injection can safely be performed. Posterior segment examination must be performed carefully before each study treatment. The results of the examination including any abnormalities (e.g. vitreous cells/haze, retinal tear/detachment, hemorrhage and vascular occlusion, vasculitis, etc.) should be recorded in the source documents. If there are any signs of IOI, vitreous cells and haze should be assessed using National Institutes of Health (NIH) grading system (Nussenblatt et al 1985). The outcome of the examination will be documented in the source document (e.g. ophthalmic examination tool) and appropriate eCRF page as applicable.
- The fundus examination and FAF will be performed at the ophthalmic exam visits indicated in the visit assessment schedule (Table 8-1) for the study eye only. Except for Screening/Baseline visit and Week 48/EOS Visit, the fellow eye will be examined at the discretion of the investigator. The results of the examination of either eye must be recorded in the source documents.

Pupil dilation for slit lamp examination and indirect ophthalmoscopy is optional according to investigator practice.

Clinically significant abnormal findings (as judged by the investigator) from the slit lamp or ophthalmoscopy observations should be recorded as an AE in the eCRF.

A phone call one week after the first injection (a window for the phone call is +7 days) must be made to check whether there are any changes in vision or any symptoms of intraocular inflammation. It should be documented in the source document. From the second injection onwards, similar phone calls should be made at investigator's discretion per local practice.

**Instruct the patient to contact the site for any changes in vision or any symptoms of inflammation between scheduled visits.** Every effort should be made to bring the subject for immediate examination.

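### SAP 2.8.2 summarises fundus autofluorescence (FAF) at Week 4, where the protocol schedules none, and omits the scheduled Week 12 FAF

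*SAP*

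**What the plan says.** SAP Section 2.8.2 (Addendum 1.0) plans two FAF summaries. The first covers whether FAF was performed, the reason if it was not, macular atrophy in the central subfield and foveal atrophy: "The number and percentage will be provided at Baseline, week 4 and end of study (week 48) for below question". The second covers the area of macular atrophy, which "will be presented at Baseline, Week 4 and Week 48 along with change from Baseline and percentage change from Baseline in FAF". Week 12 appears in neither sentence. The text of 2.8.2 is the same in SAP Amendment 2.0.

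Protocol Section 8.3.2 says that color fundus photography (CFP), FAF and fluorescein angiography "will be performed in the study eye at the visits indicated in the visit assessment schedule", meaning Table 8-1. In that table the FAF row is marked at Day 1, Week 12 and the Week 48 column, which end of study shares with early treatment discontinuation (ETD). The Week 4 cell is blank. Section 8.3.2 adds: "CFP, FAF and FA may be performed at other visits at the investigator's discretion but they are not mandatory for the study".

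For CFP, whose row in Table 8-1 has the same marks as FAF, SAP Section 2.8.1 says: "The number and percentage will be provided at Screening/Baseline, week 12 and end of study (Week 48) for below questions".

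**The concern.** The SAP tabulates a visit at which the protocol asks for no FAF, and leaves out one at which it does. Three things follow if 2.8.2 is programmed literally.

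- The Week 4 column is empty or nearly so. Because the first item asks whether FAF was done and why not, the table could read as a run of missed assessments at a visit where none was due.
- FAF completeness at Week 12, where it was due, is not shown.
- Macular atrophy, foveal atrophy and atrophy area on FAF at Week 12, with change from Baseline, are not summarised. Week 12 is the only scheduled FAF between Baseline and the Week 48/ETD column.

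**Working it through.** There is no planned figure to reproduce here. The check compares the two visit lists and asks whether any SAP rule could reconcile them.

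**1. Visit lists for the study eye**

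| Visit | Table 8-1, FAF | SAP 2.8.2, FAF | Table 8-1, CFP | SAP 2.8.1, CFP |
|---|---|---|---|---|
| Day 1 / Baseline | yes | yes | yes | yes |
| Week 4 | no | **yes** | no | no |
| Week 12 | yes | **no** | yes | yes |
| Week 48 | yes (or ETD) | yes | yes (or ETD) | yes |

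In the SAP but not scheduled: Week 4. Scheduled but not in the SAP: Week 12. The column positions in Table 8-1 can be trusted, because rows marked at every visit, such as vital signs, fill all eight columns from Day 1 to Week 48.

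**2. Could a Week 12 image be analysed as Week 4?** SAP Table 2-1 sets the Week 4 window at Day 22 to 34 and the Week 12 window at Day 71 to 97. The gap between the end of one and the start of the other is 71 − 34 = 37 days. No image can belong to both.

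**3. Could Week 4 hold any FAF data?** There are two routes, both narrow.

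- Discretionary FAF, which protocol 8.3.2 permits. The SAP keeps unscheduled visits out of by-visit tables, but an optional image taken at the scheduled Week 4 visit is not clearly caught by that rule.
- An early ETD visit. Table 8-1 footnote 11 places ETD four weeks after the last injection, and the ETD column includes FAF. A patient whose only injection was on Day 1 reaches ETD at about Day 1 + 28 = Day 29, inside Day 22 to 34. A patient with a second injection does not: loading doses are at least 21 days apart, so the earliest ETD is about Day 22 + 28 = Day 50. Section 8.3.2 also waives FAF at premature study discontinuation if one was done in the previous 12 weeks, unless disease has worsened. If that waiver is applied to ETD, a Baseline image four weeks earlier would usually satisfy it.

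**4. Is Week 4 likely to be deliberate?** For the other ocular assessments with fixed visits, the SAP's study-eye visits match Table 8-1: CFP (Baseline, Week 12, Week 48), fluorescein angiography (Week 12, with change from Baseline), indocyanine green angiography (Baseline, Week 12) and intraocular pressure (Baseline, Week 48). FAF is the only exception, and 2.8.2 gives no reason. The SAP change log shows that 2.8.2 was edited to add foveal atrophy and that a wrong Week 44 window limit was corrected elsewhere, but the FAF visit was left as it was.

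**5. Is Week 12 FAF summarised elsewhere in the SAP?** Section 2.3.4 covers FAF at Baseline only. No other SAP section gives an FAF summary after Baseline.

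**The case against.** The strongest textual defence is protocol Section 8.4.3: "The fundus examination and FAF will be performed at the ophthalmic exam visits indicated in the visit assessment schedule". The ophthalmic examination row of Table 8-1 is marked at Week 4, so one might argue that FAF is due then. This does not hold up. The sentence refers back to Table 8-1, where FAF has its own row with Week 4 blank, and footnote 3 defines the ophthalmic examination row as "Include slit lamp examination and fundus examination", without FAF. Even on the broad reading, Week 12 is also an ophthalmic examination visit, so its omission stays unexplained. The wording of 8.4.3 is nevertheless loose.

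Other limits on the point do stand. A reader might infer the following stronger claims, which the documents do not support.

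- *No FAF exists at Week 4.* None is scheduled, but discretionary or early ETD images could give a few values.
- *Atrophy at Week 12 goes unreported.* SAP 2.8.1 tabulates "Presence of atrophy in the central subfield the diameter of 3000 μm" by CFP at Week 12. What is missing is the FAF reading and the area. Week 12 FAF values may also still be listed: protocol 12.5.2 promises listings of ophthalmic examination data by visit, although SAP 2.8.2 asks for no FAF listing.
- *The Week 12 primary analysis is affected.* It is not. The primary endpoint is CNV lesion area on OCT-A, and FAF is named in no primary or secondary endpoint. The protocol describes FAF only as a means of inspecting retinal pathology, and it is read by the investigator, not the central reading center. The documents do not present atrophy as a treatment outcome of interest.
- *A known number of patients is lost.* The 189 in the sample-size section is the number needed for OCT-A precision, not an FAF count. The planned 210 patients is only a ceiling.
- *The both-eyes instruction in 2.8.2 is a separate error.* Protocol Section 8 and SAP 2.1.1 already limit fellow-eye examination to Screening/Baseline and Week 48, and 2.8.1 and 2.8.3 use the same both-eyes wording. A clarification is enough.

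**Conclusion.** The point holds as a visit-label inconsistency of minor severity. SAP 2.8.2 names Week 4 twice where protocol Table 8-1 schedules Week 12, and no window rule reconciles them. Followed literally, it yields a Week 4 FAF summary with few or no data and leaves all scheduled Week 12 FAF results out of the summaries, including the only scheduled mid-study FAF atrophy area. The number of patients concerned cannot be taken from the documents; it is at most the 210 planned, less those with no Week 12 FAF.

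The conclusion rests on reading the FAF row of Table 8-1 as governing, which Section 8.3.2 supports. That Week 4 is a slip is an inference from the agreement of the other assessments with Table 8-1. The mismatch itself does not depend on that inference.

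**What to change.** In SAP 2.8.2, replace Week 4 with Week 12 in both sentences, for the study eye. As a clarification, add that fellow-eye FAF is summarised at Baseline and Week 48 only, in line with protocol Section 8 and SAP 2.1.1. Update the FAF table shells to match.

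The cost is one word in each of two sentences, one added clause and the shell update. The protocol already collects Week 12 FAF, so no visit, assessment or sample-size change is needed. Any discretionary or early ETD image in the Week 4 window can go to a listing.
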